## **8.3 Statistical Plan and Sample Size**

The sample size was determined based on the average number of patients with bladder exstrophy who undergo closure during a calendar year at JHMI. It is estimated that 60 would be an adequate sample size. The results of this pilot study will be informally compared to previously published rates of the variables listed above for bladder exstrophy closure without the use of stereotactic imaging assistance.

Descriptive statistical analysis will be performed for all collected variables with counts, percents, median and interquartile range as appropriate. No formal statistical tests will be performed.

## **8.4 Early Stopping Rules**

No early stopping rules will be employed in this study.

# **9. Risks**

## **9.1. Risks Related to Standard Operative Procedure**

### **Surgery:**

The participant has already agreed to undergo an operation to help correct a pediatric urology issue. The risk and discomforts of the operation have already been explained and are covered under the informed consent that was signed for that particular procedure.

### **General Anesthesia:**

General anesthesia will be used during the primary operative procedure. All of the known risks associated with anesthesia apply including respiratory problems, stroke, low blood pressure, and death. Problems such as these are extremely rare in children. All anesthetic care will be directed by a certified pediatric anesthesiologist.

## **9.2. Risks Specific to Research Activities**

Soft tissue distortion that occurs during surgery or inaccuracies during registration of the virtual diagnostic images described in section 6.5 may cause the virtual image to misrepresent the patient's actual anatomy. However, this poses minimal risk to the patient as the image guidance will only be used as a supplement to direct visual inspection of patient's anatomy by the surgeon and will not be used as the primary source for visual guidance into the operating field.

Another risk is the possibility that the external fixator pins described in section 6.5 may shift from their original placement while applying the VectorVision® 2-pin fixator. Though this risk is unlikely, if this were to happen corrective measures would be taken to restore the

external fixator pins back to their appropriate position prior to continuation of the procedure.

Just as with use of any computerized equipment, there is a risk of equipment malfunction that may result in an increase in operating time. Overall, known risks are rare, but these and any unanticipated problems will be medically managed as appropriate, and reported to the IRB and FDA promptly as per DSMP.

### **9.3. Legal Risk**

There is a risk to confidentiality. Most participant related data will be stored in our institutions electronic medical record. This system requires authorized access and is password protected. Every effort will be made to keep the subjects' non-electronic records and consent forms safe by storing in a locked office. If members from the IRB or other Federal agency need to inspect records, they will be released. Hence, absolute confidentiality cannot be guaranteed. The results of this research project may be presented at meetings or in publications; however, subjects' identity will not be disclosed.

### **9.4. Financial Risk**

No additional costs to the patient are associated with the addition of VectorVision stereotactic imaging. The costs of the disposable instrumentation associated with VectorVision will be funded by the Department of Pediatric Urology.

### **9.5. Steps Taken to Minimize Risk**

Risks will be minimized through precautions set forth through standard operating room protocols, such as proper attire and scrub and monitored anesthesia. Hands will be washed before performing any invasive procedure. Personnel will follow "Universal/Standard Precautions" to prevent and minimize exposure to blood and body fluids. Personnel will wear standard operating room attire, which shall consist of a clean scrub suit, disposable surgical mask and cap. A surgical mask that fully covers the mouth and nose will be worn when entering the operating room (if sterile instruments are exposed or the operation is about to begin or is underway).

Every effort will be made to maintain participant confidentiality throughout the trial. Measures to help ensure protection include use of password-protected Excel spreadsheets for all study data. Patient study records will be kept in a locked office accessible to IRB approved study staff.

MRI registration errors and the possibility of soft tissue distortion that may occur to soft tissue as the result of the surgical procedure can lead to inaccuracies with the imaging system. Extra care will be taken to verify that anatomical structures that can be seen with the surgeon's eyes match up to the equivalent landmarks seen on the VectorVision system's virtual image to minimize risk of surgical error.

## **10. Benefits**

This study may benefit participants through more precise surgical dissection, yielding better outcomes and reduced complications

Classic bladder exstrophy is one of the largest birth defects affecting 1 out of 30,000 children that is correctable with surgery. Classic bladder exstrophy is where the bladder of a child, as well as the

abdominal wall and genitalia are not formed properly. Johns Hopkins is the leading center in the world for correction and research on this birth defect. Developing methods for other surgeons at centers with less experience to better understand and identify the anatomy involved with this surgery may help improve the success of the surgery worldwide.

## 11. Data and Safety Monitoring Plan

The research involves some risks to the participants. A group of designated faculty, that includes Pediatric Orthopedic Surgeon [name], Pediatric Anesthesiologist [name], and Adult Urologist [name] [name], will be involved in safety monitoring. These individuals will be notified promptly for any serious adverse events or deaths and will perform routine monitoring and oversight reviews of the research and postoperative outcomes to assess for trends or risks that were not previously identified. In the event of an adverse event, unanticipated problem, or a study deviation the IRB will be notified within 24-48 hours and the research will be halted pending review. Per the Johns Hopkins IRB policy 103.6b, "Unanticipated problems involving risks to participants or others" is defined as: The information is unexpected in terms of nature, severity, or frequency, given:

- a. The research procedures described in the protocol and informed consent document; and
- b. The characteristics of the subject population being studied; and
- c. The information indicates that participants or others are at greater risk of harm (including physical, psychological, economic, or social harm) than was previously known or recognized.

Also as per policy, the prompt reporting of unanticipated problems or events will occur as soon as possible after the PI learns of the event, but in all cases within 10 working days with the exception of death of a participant which must be reported within 3 working days.

Additionally, a team of designated faculty, including the PI's clinical fellow, the orthopedic surgeon ([name]), and the radiologist ([name]), will be present to monitor the patient during surgery. Standard safety monitoring by the anesthesiology team during surgery and post-operative nursing staff will monitor the patient for any safety concerns related to the surgery or immediate post-operative care.

### 11.1 Adverse Events

An adverse event (AE) is defined as an unusual and undesirable symptom or sign that occurs in participants during the clinical study. Adverse events include those clinically significant laboratory values and test results, concomitant illness, accident, medical occurrence or worsening of existing medical condition that emerge during study participation.

### 11.2 Adverse Event Grading

The investigator will evaluate the severity of each adverse event using the following definitions:

- *Mild* - event may be noticeable to subject; does not influence daily activities; usually does not require intervention.
- *Moderate* - event may be of sufficient severity to make subject uncomfortable; performance of daily activities may be influenced; intervention may be needed.

- *Severe* - event may cause severe discomfort; usually interferes with daily activities; subject may not be able to continue in the study; treatment or other intervention usually needed.

All participants will receive pre-op, operative, and post-operative care according to the standard of care at Johns Hopkins. Given the broad array of postoperative adverse events associated with an extensive surgery of this nature, AEs graded as ‘severe’ which are possibly, probably, or definitely attributable to the use of the investigational device will be recorded and monitored until the event has resolved to meet the definition of ‘mild’. All participants will receive care for all adverse events according to good clinical practice as per the standard of care at Johns Hopkins.

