The stereotactic imaging (which can be viewed in 3 dimensions) will be displayed on a monitor in the operating room in real time. The VectorVision® system has several sterile instruments and probes that can be used to visualize where the instrument is in real-time. This capability will allow for stereotactic imaging, confirmation that the anatomical structures of interest have been identified by both the surgeon's eyes in the operative field and the radiologist's eyes on the image monitor and thus allow for placement of the instruments during dissection of the pelvic floor.

Once the pelvic floor has been properly identified with stereotactic confirmation, the VectorVision® device will no longer be used. The reference array will be removed from the external fixation pins on the patient, and surgery will continue as it routinely does during standard clinical practice.

Postoperatively, the patient will receive routine clinical postoperative care which includes placement in traction and the use of an external fixator to prevent separation of the pubic bones as per standard of care. A suprapubic tube as well as ureteral stents is also left in place. Prophylactic antibiotics are continued post-operatively to prevent renal scarring from vesicoureteric reflux that is usually present and the hospital stay will be three to four weeks. Prior to discharge from the hospital the suprapubic tube will be removed and the patient will be schedule to follow up at routine clinical visits that typically occur at 2 weeks, 1 month, 3 months, 6 months, and 12 months after discharge from the hospital.

Outcomes, including success or failure of exstrophy closure, urinary continence, operative time, length of hospital stay, and a record of all peri-operative and post-operative complications, will be collected quarterly from the patient's medical record from all follow up visits for the 12 months following the surgical procedure.

No change in participant's care will occur if the study ends or the participant withdraws.

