### **11.5 Plan for data collection and AE reporting**

Study outcomes, including success or failure of exstrophy closure, urinary continence, operative time, length of hospital stay, and a record of all peri-operative and post-operative complications, will be collected quarterly by IRB approved study staff from the patient’s medical record for 12 months post procedure.

Operative complications will be defined as complications that may be a direct effect of the quality of the operative procedure. Failure of exstrophy closure is defined as either a post-operative dehiscence, bladder prolapsed, or a vesicocutaneous fistula. These outcomes will be compared to previously established rates of success, complications, continence, etc.

Only those AE’s deemed as possibly, probably or definitely attributable to use of the investigational device will be collected and reported at the time of the annual IRB continuing renewal.

If a serious adverse event (SAE) occurs, the study investigator will complete and submit the Unanticipated Problem form or Problem/Event reporting mechanism via the eIRB. The investigator will also compile with urgent priority other relevant documentation (e.g., copies of test results,

hospital discharge summary, autopsy report, etc.). The IRB will be informed of all required SAE's within ten (10) days as per JHM IRB and institutional guidelines.

Serious adverse events will be reported to the FDA at the discretion of the principal investigator via the FDA Med Watch 3500 voluntary reporting mechanism.

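### Section 11.2 ties recording of device-attributable adverse events to a severe grade while 11.5 sets no severity limit, so lesser device events can go unrecorded

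*Combined protocol and SAP*

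**What the plan says.** The relevant rules are spread over several sections of the combined protocol and SAP.

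- **11.2 Adverse Event Grading** defines mild, moderate and severe, then states that "AEs graded as ‘severe’ which are possibly, probably, or definitely attributable to the use of the investigational device will be recorded and monitored"; follow-up ends once the grade has come down to mild. The same sentence gives the reason: "Given the broad array of postoperative adverse events associated with an extensive surgery of this nature".
- **11.5 Plan for data collection and AE reporting** says: "Only those AE’s deemed as possibly, probably or definitely attributable to use of the investigational device will be collected and reported", at the annual IRB renewal. The restriction is by attribution; severity is not mentioned.
- **Section 11, opening paragraph**, requires IRB notice within 24-48 hours and a halt of the research pending review for an adverse event, an unanticipated problem or a deviation. It limits this neither by severity nor by attribution.
- **11.1 Adverse Events** begins "An adverse event (AE) is defined as an unusual and undesirable symptom or sign"; its next sentence also counts accidents and medical occurrences.
- **9.2** names three research-specific risks: a virtual image that misrepresents the anatomy, the chance that "the external fixator pins described in section 6.5 may shift from their original placement while applying" the 2-pin fixator, and equipment malfunction that lengthens the operation. It promises prompt reporting to the IRB and FDA, in line with the monitoring plan.
- **2.1a** makes device safety a primary objective. **8.3** plans descriptive statistics without formal tests, and **8.4** has no early stopping rules.

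**The concern.** The safety evidence on the device will be a set of counts from a single-arm study. Those counts mean little unless it is clear which events were to be written down. A site that follows 11.2 could leave out every device-attributable event below severe and believe that it had complied. A site that follows 11.5 would include them.

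The grading wording adds to the difficulty, because the device is used only during the operation. A mild event is one where the "event may be noticeable to subject; does not influence daily activities; usually does not require intervention". Noticeability, discomfort and daily activities are hard to apply to a child under general anaesthesia. Afterwards, "routine clinical postoperative care which includes placement in traction and the use of an external fixator" restricts activity in every child during a stay of three to four weeks. Whether an intra-operative device event reaches severe is therefore largely a matter of judgement, and under 11.2 that judgement may decide whether the event is recorded at all.

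**Working it through.** The plan states no AE rate, safety threshold or precision target tied to 11.2, so there is no figure to reproduce. The check is mainly a comparison of text.

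**Step 1: the rules side by side, for an event attributed to the device**

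| Section | Severity limit | Consequence |
|---|---|---|
| 11.2 | severe | recorded, followed until mild |
| 11.5 | none | collected, reported annually |
| 11, opening | none | IRB notice in 24-48 hours, research halted |
| 9.2 | none | prompt report, as the monitoring plan provides |

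A moderate device-attributable event is outside the 11.2 rule, inside 11.5, and a halt trigger under the opening of section 11. These cannot all be applied together if 11.2 defines what is recorded.

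**Step 2: does the stated reason need a severity limit?** The reason in 11.2 is the many AEs expected after major surgery. Restricting the record to device-attributable events already removes those judged unrelated or unlikely under 11.4. The severe limit then acts on events that someone has linked to the device, which are the ones objective 2.1a concerns.

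**Step 3: a test case.** Take a pin shift put right in theatre. The activity criteria give no answer. The intervention criterion does apply, but it separates moderate (intervention may be needed) from severe (usually needed) only by degree. Either grade is defensible. If the grade is moderate, 11.2 does not require a record.

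**Step 4: other routes by which the 9.2 events might be captured**

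- The 9.2 reporting promise defers to the monitoring plan, which is section 11 itself.
- Unanticipated problems must be unexpected given the protocol. Events listed in 9.2 are hard to place there.
- Peri-operative complications are an outcome in 4.3a. But 11.5 links operative complications to the quality of the procedure and takes outcomes quarterly from the medical record, and 8.1 lists no device-event or intra-operative event rate.
- Added operative time (8.1) would reflect a long malfunction but not its cause.
- Section 9.5 calls for visible landmarks to be matched to the image, but asks for no record of a mismatch.

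No section describes a data field for pin shift, registration mismatch or malfunction.

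**Step 5: illustration on assumed inputs.** Let *p* be the true proportion of children with a device-attributable AE and *s* the share of those graded severe. Neither is in the documents. With n = 60 (section 4.1) and independent children, the chance of recording at least one event is 1 − (1 − ps)^60.

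| p | s = 1 (no limit) | s = 25% | s = 10% |
|---|---|---|---|
| 2% | 70.2% | 26.0% | 11.3% |
| 5% | 95.4% | 53.0% | 26.0% |
| 10% | 99.8% | 78.1% | 45.3% |

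For example, p = 5% and s = 25% give ps = 0.0125 and 1 − 0.9875^60 = 53.0%.

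If no event is recorded in 60 children, the one-sided 95% upper bound is 1 − 0.05^(1/60) = 4.9%. Under the restrictive reading of 11.2 that bound covers severe attributable events only.

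**The case against.** The strongest reply is that 11.2 never says *only*. Its sentence joins recording with monitoring until the event is mild, so it can be read as a follow-up rule for the worst events, leaving collection to 11.5, whose title is data collection and AE reporting. In support, 11.2 has every AE graded and 11.4 has every AE attributed. This stands as far as it goes: the restrictive reading is the more natural one given the stated reason, but it is not certain. The ambiguity itself needs removing.

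Four stronger conclusions that a reader might draw are not supported.

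- *That the scale cannot grade these children.* Every grade has an intervention criterion, and moderate and severe have discomfort criteria. Subjects are aged 0-7 years, and follow-up of 12 months outlasts traction. The scale is poorly suited to events under anaesthesia; it is not unusable.
- *That 11.1 excludes the 9.2 harms as neither symptom nor sign.* Its second sentence admits accidents and medical occurrences, and a displaced pin plausibly fits.
- *That the 9.2 harms are screened out altogether.* A corrected pin shift is not shown to be at most moderate, since correction is an intervention. Section 11.5, the opening of section 11, the 9.2 promise and the added-time outcome are partial routes to capture.
- *That some number of events would be missed, such as 3 to 6 in 60.* That takes rates of 5% to 10% (0.05 × 60 = 3; 0.10 × 60 = 6), assumes none is graded severe, and ignores 11.5. The documents give no rates; 9.2 calls pin shift unlikely and known risks rare.

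**Conclusion.** The point holds as a conflict between sections with a consequence for a primary objective. Sections 11.2 and 11.5 set different severity limits for the same device-attributable AEs, and the opening of section 11 sets none. If 11.2 is read restrictively, and if some device events are graded below severe, those events can be missing from the record and the reported device-event rate will be too low. The other capture routes narrow this gap without closing it.

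The direction of the error follows from the text; its size does not. The probabilities above rest on assumed values of *p* and *s*. They show only that a severity limit can matter at this sample size, and are not an estimate for this trial. The conclusion does not depend on them.

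**What to change.** 1. In 11.2, state that AEs possibly, probably or definitely attributable to the device are recorded at every grade, as in 11.5. Keep severe only as the threshold for follow-up until mild.
2. Add operative-form tick-boxes for the 9.2 events: pin shift, registration or landmark mismatch, and equipment malfunction. Complete them at surgery, whatever grade is assigned.
3. In section 8, report the count of each over all children in whom the reference array was attached.
4. Log these as device events, and reconcile this with the notification and halt wording that opens section 11, so that all passages agree on which events trigger it. Without this step, each logged mismatch or brief malfunction could be taken to require a halt.

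The cost is a sentence in 11.2, a short addition to one form and to section 8, and the reconciliation in section 11. Study staff are already in theatre to complete the form. The reported device-event rate will be somewhat higher, and there is slightly more form-filling. The existing severity scale can stay, because recording would no longer depend on it.

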### **11.3 Serious Adverse Events (SAE)**

A serious adverse event will be defined as any adverse event that:

- Results in death
- Is immediately life-threatening – an adverse event which places the subject/patient at immediate risk of death from the adverse event as it occurred
- Results in permanent or substantial disability
- Results in or prolongs an existing in-patient hospitalization

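### The serious adverse event definition in 11.3 has no criterion for a device injury that needs corrective intervention, so such an injury need not trigger prompt notice to the safety faculty

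*Combined protocol and SAP*

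**What the plan says.** Section 11.3 makes an adverse event serious if it meets any one of four criteria:

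- death;
- "Is immediately life-threatening";
- "Results in permanent or substantial disability";
- "Results in or prolongs an existing in-patient hospitalization".

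The need for treatment or intervention appears only in the severity grades of 11.2, which do not decide seriousness.

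Seriousness controls one route in particular. Of the designated safety faculty, section 11 says: "These individuals will be notified promptly for any serious adverse events or deaths". It also gives them routine oversight reviews, without a frequency or a list of what they receive.

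Section 5 has the device in use only until the pelvic floor has been identified, after which the reference array comes off. It adds that "the hospital stay will be three to four weeks". Section 9.2 foresees a virtual image that does not match the true anatomy, and fixator pins that move while the array is being attached. Of the pins it says that "if this were to happen corrective measures would be taken to restore the" pins before the operation goes on. Section 9.5 mentions surgical error in connection with imaging inaccuracy.

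The reporting times differ from place to place. Section 9.2 promises prompt reporting of the known risks to the IRB and FDA. Section 11 sends any adverse event to the IRB in 24 to 48 hours and halts the research pending review. Section 11.5 says that adverse events at least possibly attributable to the device "will be collected and reported at the time of the annual IRB continuing renewal", and gives ten days for serious ones.

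**The concern.** A device that acts only during an operation tends to show its harm there, as an injury that is seen and repaired, or soon afterwards, as an unplanned return to theatre. A seriousness list without an intervention criterion can miss both. The only one of the four criteria that a repaired, non-threatening, non-disabling injury could readily meet is a longer stay, and every child is already expected to be in hospital for weeks.

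At stake is the timeliness of information to the safety faculty. Under 4.1b they may remove a child from the study on safety grounds and must judge whether treatment failures result from the intervention. Section 8.4 provides no early stopping rules, so their judgement carries more weight. Safety of the device is half of primary objective 2.1a.

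**Working it through.** No figure in the plan bears on this point, so the check sets the definition against the foreseeable events, and then each reporting route against the events that fall outside it.

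**Step 1: events against the four criteria.**

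| Event | Meets a criterion in 11.3? |
|---|---|
| Fixator pins shift and are restored in the same operation | No, if there is no threat to life, lasting disability or longer stay |
| Injury from dissection guided by a misregistered image, repaired in the same operation | No, on the same conditions |
| Unplanned return to theatre during the planned stay | Only if the stay is recognised as prolonged |
| Unplanned re-operation after discharge that needs admission | Yes, hospitalization |
| Injury that threatens life or disables | Yes |

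**Step 2: how well the hospitalization criterion works.** Input: the planned stay of three to four weeks (section 5).

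- Range of the planned stay: 4 × 7 − 3 × 7 = 28 − 21 = 7 days.
- No expected discharge date is defined for the individual child. A return to theatre that adds up to 7 days to what would have been a 21-day stay still ends by day 28, inside the planned range, and need not be recognised as prolongation.
- A repair in the same operation may add no days at all.

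**Step 3: routes left for an event in the first three rows.**

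- *Prompt notice to the safety faculty (section 11).* Limited to serious events and deaths, so not triggered.
- *Routine faculty reviews (section 11).* They could show the event, but at no stated interval and from no stated data.
- *Faculty judgement on treatment failures (4.1b).* Section 11.5 defines failure of closure as dehiscence, prolapse or vesicocutaneous fistula. An injury repaired on the table is none of these unless it later leads to one.
- *Outcome data (11.5 and 11.6).* Complications are collected quarterly and the PI reviews the data quarterly. Neither section says that the data go to the faculty.
- *IRB, 24 to 48 hours with a halt (section 11), and IRB and FDA promptly (9.2).* These apply on their wording, but neither names the safety faculty.
- *IRB, annual renewal (11.5).* This applies to the same device-attributable events, on a very different clock. Section 9.2 defers to the safety monitoring plan, of which 11.5 is part, so it does not settle the matter.

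**Step 4: the definition of an adverse event.** Section 11.1 opens: "An adverse event (AE) is defined as an unusual and undesirable symptom or sign that occurs in participants during the clinical study". Read alone, the word for rarity could leave out an excess of ordinary complications. The sentence after it is broader and takes in any medical occurrence that emerges during participation. This is a mismatch of wording rather than a second clear filter.

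**The case against.** The strongest answer is that prompt oversight exists elsewhere. Section 9.2 lists the very hazards at issue and then promises prompt reporting of them to the IRB and FDA. Section 11 goes further and halts the research after any adverse event. The faculty also see more than serious events: they review postoperative outcomes for trends and judge whether closure failures stem from the intervention. A designated team that includes an orthopedic surgeon and a radiologist watches the operation itself. Repeat surgery is a primary outcome variable in 8.1, and all complications are recorded. Section 9.2 also rates the imaging risk as minimal, because direct vision remains the primary guide, and calls a pin shift unlikely.

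Most of this stands, and it rules out three stronger readings that a reader might infer.

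- *That the safety faculty are never told of such injuries.* The documents do not say this. What is missing is the trigger for prompt notice.
- *That only the annual report remains.* Section 11.5 can be read that way on its own, but 9.2 and section 11 say otherwise.
- *That a given number of further children would be operated on before anyone acts.* Any such figure presumes that the annual clock prevails over the 24 to 48 hour clause and the halt. The text does not establish that.

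The objection does not supply the missing criterion. None of the other routes gives the faculty prompt notice of a repaired device injury, and the two IRB clocks conflict.

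**Conclusion.** The point holds as a gap in a definition. Section 11.3 lacks a criterion for events that need intervention to repair injury or prevent lasting harm. A device injury repaired in theatre, or re-operated within the planned stay, can therefore fall outside all four criteria, and the safety faculty need not be told of it promptly.

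The gap is confined to injuries that do not threaten life, disable or prolong the stay, since the others are already serious. Its size cannot be put as a number: the documents give no rate for such injuries and do not make clear which reporting clock applies. The conclusion assumes that 11.3 is applied as written and that the faculty's routine reviews are not, in practice, close enough together to serve as prompt notice. It is worth correcting because the omission falls on the kind of harm that the protocol itself foresees, and the correction is small.

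**What to change.** 1. Add a fifth criterion to 11.3: an event rated possibly, probably or definitely related to the device under 11.4 that requires unplanned intervention, including repair during the operation or an unplanned return to the operating room, to correct injury or prevent permanent impairment. The existing prompt notice to the safety faculty then applies without further change.
2. Reconcile the reporting times in 9.2, section 11 and 11.5, so that one device-attributable event cannot fall under both the short IRB clock and the annual renewal. The criterion alone does not resolve this.
3. Optionally, drop the requirement in the first sentence of 11.1 that an event be unusual, so that it agrees with the sentence that follows.

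The device-attribution condition matters. Section 4.1b cites closure failure as high as 63%, so a criterion covering every unplanned intervention could make many ordinary complications serious events. With the condition, the cost is some additional prompt reports, which also come under the ten-day IRB rule for serious events in 11.5. No visits, procedures or data collection are added, and clinical care is not affected.
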